5.3. EXCLUSION CRITERIA

1. History of other malignancy (with the exception of squamous cell or basal cell carcinoma of the skin) diagnosed within the last 3 years
2. Intention to enroll in a blinded therapeutic clinical trial

5.4. INCLUSION OF WOMEN AND MINORITIES

Males of all races and ethnic groups are eligible for this study and encouraged to participate. Women are excluded by virtue of the pathology being studied.

6. SUBJECT RECRUITMENT AND INFORMED CONSENT

Urologists at Johns Hopkins will be educated about the study including patient eligibility criteria. At the treating physician's discretion, patients will in turn be educated about the study and their interest in participation assessed. Any patient who expresses interest in participating in the study will then either be directly introduced to the study team staff, who will be present on select days in the urology clinic, or provided with the contact information of the study coordinator. Alternatively, patients learning about the protocol on ClinicalTrials.gov may contact the study coordinator directly. In all cases, as much time as is needed to consider study participation will be allowed to possible participants; resulting in multiple phone calls, visits, emails, or other communication, as necessary.

The principal investigator or designated individual will discuss the study with interested patients. Patients will be provided with the Institutional Review Board (IRB) approved consent form for review and given sufficient time to consider participation in the study. Once a decision has been made to enter into the study, a signature will be obtained from the patient to confirm consent.

Patients may voluntarily withdraw consent at any point following enrollment in the study. At the time of informed consent patients will be instructed that they may withdraw consent by contacting the principal investigator or study coordinator.

7. RISKS & BENEFITS

7.1. RISKS

¹⁸F-DCFPyL is a novel imaging agent, which to date, has been studied in only 9 men with advanced prostate cancer under IRB protocol NA_00092956. Despite this small number, the compound appears to be very well tolerated with no reported serious adverse related events.

During the course of this study patients will be exposed to 3.18 rem (1.59 rem per PET/CT) of radiation.

The risks related to both DCFPyL and radiation exposure will be explained to the patient during the informed consent process.

7.2. BENEFITS

By participating in this research study, patients and their physicians will have access to the results of the PET/CT scans which may be used to personalize an individual patient's cancer treatment plan.

8. STUDY PROCEDURES

1. Eligibility screening and informed consent
2. ¹⁸F-DCFPyL PET/CT scan performed within 45 days of latest PSA, bone scan and cross-sectional imaging
3. Assessment of adverse events via phone call at 1-3 days following PET/CT
4. Management per the treating physician including periodic PSA measurements and re-staging imaging as clinically indicated
5. ¹⁸F-DCFPyL PET/CT scan performed 6 months following the first PET/CT (window -1 to +2 months)
6. Assessment of adverse events via phone call at 1-3 days following PET/CT
7. Collection of PSA, imaging and treatment data generated as part of routine clinical care for up to three years following the second ¹⁸F-DCFPyL PET/CT

9. PROTOCOL FOR ¹⁸F-DCFPYL PET/CT

1. Patient will fast for 4 to 6 hours prior to injection of ¹⁸F-DCFPyL
2. An intravenous peripheral intravenous catheter will be placed (or an upper-extremity existing central line accessed) in order to inject the radiotracer
3. Intravenous fluid (5% dextrose + 0.45% normal saline) will be delivered at a low flow rate during the duration of the study (maximum 2 liters)
4. A bolus of less than or equal to 9 mCi (333 MBq) of ¹⁸F-DCPyL will be injected into the IV line by slow push
5. At approximately 60 minutes after the administration of ¹⁸F-DCFPyL, IV fluids will be discontinued and the patient will be asked to void. A whole-body CT and PET scan will then be acquired from the mid-thigh to the vertex of the skull. The PET/CT will be performed on a Discovery DRX PET/CT scanner (GE Healthcare) operating in 3-dimensional emission acquisition mode. Scans will include approximately 8 to 9 fields-of-view, depending on patient height.
6. Temporary IV access will be removed

10. STUDY STATISTICS

Descriptive statistics (i.e. proportions/percentages for categorical variables and medians with interquartile ranges for continuous variables) will be used to detail the study cohort and findings on ¹⁸F-DCFPyL PET/CT. More specifically, we plan to report data individually and in aggregate for patient age, race/ethnicity, TNM stage, pathologic Gleason score, surgical margin status, prior cancer treatment and interval treatment following the first PET/CT scan. Additionally we will report the number and location of putative sites of disease detected on PET/CT for both time points. These putative sites will be correlated to findings on available bone scan and cross-sectional imaging obtained during the course of routine clinical care and their rate of concordance reported with 95% confidence intervals. Similarly, we plan to correlate findings on PET/CT scan with the tissue histology and PSMA expression (as determined by immunohistochemistry) of pathology specimens collected in follow-up as part of routine clinical care. Finally, we plan to evaluate change in the number, size and SUV_{max}/SUV_{mean} values of putative sites of disease following 6 months of therapy as prescribed by the treating physician. For this analysis, paired scans will analyzed with the McNemar's test for categorical variables and the Wilcoxon signed-rank test for continuous variables. As an additional secondary endpoint, PET/CT findings will be correlated with serial PSA values as well as time to disease progression.

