5. PATIENT SELECTION & ELIGIBILITY

5.1. NUMBER OF PATIENTS

This study aims to enroll 50 participants.

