5.2. INCLUSION CRITERIA

1. Age \geq 18 years
2. History of adenocarcinoma of the prostate treated with radical prostatectomy
3. Serum PSA level \geq 0.2 ng/mL at least 45 days prior to study enrollment
4. Completed staging evaluation with bone scan as well as CT or MRI of the abdomen and pelvis at least 45 days prior to study enrollment

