13. DISCLOSURE OF DATA

The results of each ¹⁸F-DCFPyL PET/CT will be made available to both patients and treating physicians. Because this is a novel diagnostic test, all will parties requesting scan data will be explicitly reminded as to the experimental nature of the results. Additionally, at the time of informed consent, it will be explained to patients that the results of these scans may prompt additional confirmatory imaging and/or invasive procedures that would not have otherwise been contemplated had the patient not participated in this study.

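### The plan does not require the PET/CT to be read independently of conventional imaging or of the earlier scan, so concordance and the paired change in site number may be biased by reader knowledge

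*Combined protocol and SAP*

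**What the plan says.** - **Order of tests at baseline.** Section 5.2 makes prior conventional imaging a condition of entry: "Completed staging evaluation with bone scan as well as CT or MRI of the abdomen and pelvis". Section 8, item 2 ties the first PET/CT to that imaging: "scan performed within 45 days of latest PSA, bone scan and cross-sectional imaging".
- **Comparison.** Section 10 states "These putative sites will be correlated to findings on available bone scan and cross-sectional imaging obtained during the course of routine clinical care", with "their rate of concordance reported with 95% confidence intervals". Concordance is the only quantity in Section 10 with a stated confidence interval. The unit of analysis and the interval method are not given.
- **Paired scans.** Section 10 also compares the number, size and SUV of sites between the two PET/CTs, using McNemar's test and the Wilcoxon signed-rank test.
- **Between the scans.** Section 8, item 4 reads "Management per the treating physician including periodic PSA measurements and re-staging imaging as clinically indicated". Section 13 says the results of each "PET/CT will be made available to both patients and treating physicians", and that "the results of these scans may prompt additional confirmatory imaging and/or invasive procedures".
- **Reading rules.** Section 9 covers preparation, injection and acquisition, and ends when IV access is removed. No section says who reads the PET/CT, when, with what information, or what makes a site positive or equivocal.

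**The concern.** A concordance rate describes two tests only if each is read without knowledge of the other. Here one test is complete before the other is done, and nothing stops the PET reader from opening its reports first. A faint focus may be called because the bone scan showed something there. Agreement then says less about the tracer than it appears to.

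The 6-month comparison has a similar weakness. A reader who knows the first scan and the treatment given may call or omit sites in line with what is expected. Size and SUV are measurements and less open to expectation than counts, but which sites are measured is still the reader's decision.

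The study is descriptive, so its estimates are its main product. A larger sample would not remove this error. Once only an informed site list has been recorded, an independent one can be recovered only by re-reading.

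**Working it through.** **1. What can be reproduced.** The only relevant design figure is the sample size in Section 5.1 ("This study aims to enroll 50 participants"). No expected concordance, target precision or reader effect is stated, so neither the 50 nor the size of any bias can be derived. Everything below is illustration under stated assumptions.

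**2. Inputs.** Appendix B (9 men with metastatic disease) gives 138 definite lesions on PET/CT and 30 on combined conventional imaging. With equivocal lesions the totals are 138 + 1 = 139 and 30 + 15 = 45. Assumed: an independent PET read finds a share *p* = 60% to 80% of conventional sites, and an informed reader upgrades a share *u* = 25% to 50% of the rest.

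**3. PET sites as denominator.** This is closest to Section 10, which starts from the PET sites. Even if every conventional site were also a PET site, concordance could not exceed 30/138 = 22% (definite) or 45/139 = 32% (with equivocal).

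With *P* PET sites and *C* conventional sites, the independent rate is *pC/P*. Upgrading adds *b* = (1 − *p*)*uC* sites to both numerator and denominator, so the informed rate is (*pC* + *b*)/(*P* + *b*).

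| Counts | *p* | *u* | Independent | Informed | Shift (points) |
|---|---|---|---|---|---|
| 138 and 30 | 0.80 | 0.25 | 24/138 = 17.4% | 25.5/139.5 = 18.3% | +0.9 |
| 138 and 30 | 0.70 | 0.50 | 21/138 = 15.2% | 25.5/142.5 = 17.9% | +2.7 |
| 138 and 30 | 0.60 | 0.50 | 18/138 = 13.0% | 24/144 = 16.7% | +3.6 |
| 139 and 45 | 0.80 | 0.25 | 36/139 = 25.9% | 38.25/141.25 = 27.1% | +1.2 |
| 139 and 45 | 0.60 | 0.50 | 27/139 = 19.4% | 36/148 = 24.3% | +4.9 |

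The shift is about 1 to 5 points.

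**4. Conventional-positive sites as denominator.** The informed rate is *p* + (1 − *p*)*u*.

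- *p* = 0.60: 0.60 + 0.40 × 0.25 = 0.70, and 0.60 + 0.40 × 0.50 = 0.80.
- *p* = 0.70: 0.70 + 0.30 × 0.25 = 0.775, and 0.70 + 0.30 × 0.50 = 0.85.
- *p* = 0.80: 0.80 + 0.20 × 0.25 = 0.85, and 0.80 + 0.20 × 0.50 = 0.90.

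The shift is 5 to 20 points.

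**5. Direction.** Steps 3 and 4 allow only upward movement. More generally, let *c* be the true concordance, *f* the share of discordant results turned concordant, and *g* the share of concordant results turned discordant. Then observed = *c* + (1 − *c*)*f* − *cg*.

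- *c* = 0.60, *f* = 0.20, *g* = 0: 0.60 + 0.08 = 0.68.
- *c* = 0.60, *f* = 0, *g* = 0.20: 0.60 − 0.12 = 0.48.
- *c* = 0.50, *f* = *g* = 0.10: 0.50 + 0.05 − 0.05 = 0.50, no net shift.

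**6. Interval.** Assume one result per patient, n = 50, and the Wald width 2 × 1.96 × √(*c*(1 − *c*)/50). A move from 0.30 to 0.44 changes the width from 0.254 to 0.275. A move from 0.60 to 0.68 changes it from 0.272 to 0.259. The interval is displaced, and its width may rise or fall. For scale, the Wilson 95% interval for 30/50 is 0.462 to 0.724, about 13 points either side.

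**7. The 6-month comparator.** The fixed order of tests holds at baseline only. Re-staging after the first PET/CT is done as clinically indicated, after that scan's results have been disclosed, and may be prompted by them. Dependence can then also run from PET/CT to conventional imaging.

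**The case against.** A reader might infer that the PET/CTs are read unmasked, that concordance is inflated, and that the inflation is 5 to 20 points. The documents do not support these readings.

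- **Conduct.** The plan is silent on masking. It does not say that reading is unmasked or when it takes place. Only the absence of a rule can be shown.
- **Direction.** Section 3 expects PET/CT to show far more sites than conventional imaging. A reader who shares that expectation could add PET-only sites, which lowers concordance.
- **Size.** The 5-to-20-point range needs conventional-positive sites as denominator, while Section 10 starts from PET sites. On that reading the same assumptions give about 1 to 5 points. Appendix B describes men with metastatic disease. Section 3 calls conventional imaging inadequate for small-volume disease, so in this trial there may be fewer known lesions to upgrade.
- **Stakes.** This is a descriptive pilot of 50 men, and no hypothesis test or decision rule rests on concordance. Results are deliberately open to treating physicians.
- **Limits of masking.** Section 9 includes a whole-body CT in every study scan, so a masked reader still sees anatomy that overlaps the comparator CT.

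All five points stand, and they limit the strength of the claim. They do not remove the gap, because nothing in the plan secures a PET read independent of its comparator. Disclosure is compatible with masking: the clinical report can still be fully informed once the research list is locked.

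**Conclusion.** The point holds as a gap in the plan. Independent reading is not required at baseline or at 6 months, so the concordance rate and the paired change in site number may be biased by reader knowledge. For concordance, upward bias is plausible but not established. The reported interval would shift with the estimate and carry no sign of the error.

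The size is unknown. The illustrations of about 1 to 5 points (PET sites) and 5 to 20 points (conventional-positive sites) rest on assumed values of *p* and *u*, on upgrading alone, and, for the first, on lesion counts from a different population. Because the plan does not fully define the denominator, neither range can be called the expected bias.

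The consequence is moderate. No decision depends on concordance, but it is a listed endpoint, and the correction is cheap if made before scans are read.

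**What to change.** Add to Sections 9 and 10:

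1. Whoever reads the study PET/CT first records and locks a site list for each scan (number, location, definite or equivocal). This is done without the bone scan, CT/MRI images or reports, PSA or interval treatment. For the second scan, the first PET/CT and its site list are also withheld.
2. Only then are the other images and data opened, for lesion matching and the clinical report.
3. Concordance and paired counts use the locked lists.
4. The primary concordance estimate uses the baseline conventional reads issued before the first PET/CT. Concordance at 6 months is reported separately, with a note that re-staging may have been prompted by the disclosed first PET/CT.

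The cost is protocol wording, a short locked read form and a slightly slower two-step read. No extra scan is needed. The procedure itself needs no second reader, although the documents do not say how reading is staffed.

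### Section 10 does not separate conventional scans acquired before the first PET/CT from later ones, and two 45-day rules leave the pre-PET comparator undefined

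*Combined protocol and SAP*

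**What the plan says.** Section 10 (Study Statistics) reports the number and location of "putative sites of disease detected on PET/CT for both time points". It correlates those sites with "findings on available bone scan and cross-sectional imaging obtained during the course of routine clinical care" and attaches 95% confidence intervals to the concordance rate. It does not say which conventional scan is paired with which PET/CT, which one counts when a man has several, or whether scans from before and after the first PET/CT are kept apart. Tissue has its own sentence and comes from "pathology specimens collected in follow-up as part of routine clinical care".

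Four other passages bear on this:

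- **Section 13** releases each PET/CT result to patients and their physicians, and warns that results "may prompt additional confirmatory imaging and/or invasive procedures that would not have otherwise been contemplated".
- **Section 7.2** describes results "which may be used to personalize an individual" patient's treatment.
- **Section 8, items 4 and 7** leave re-staging imaging to clinical need and provide for "Collection of PSA, imaging and treatment data generated as part of routine clinical care for up to three years following the second" PET/CT.
- **Section 5.2, criterion 4, and Section 8, item 2** govern timing. The first requires a bone scan and "CT or MRI of the abdomen and pelvis at least 45 days prior to study enrollment". The second requires PET/CT "performed within 45 days of latest PSA, bone scan and cross-sectional imaging".

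**The concern.** Concordance with conventional imaging is a listed endpoint (Sections 1 and 4). It is most easily interpreted when the comparator was acquired without knowledge of the PET/CT result. Once a result is released, a later bone scan or CT may be ordered because of it, or may show disease already altered by treatment chosen in its light. By the protocol's own account, then, some later scans may be partly a consequence of the test under study.

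Section 10 draws on whatever imaging is available and makes no distinction by timing, so the reported rate could combine the two kinds of comparison. A reader could not tell how much agreement was present before anyone had seen a PET/CT. The pairing rule could also be chosen after the data are known.

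The obvious remedy is to use the scans acquired before the first PET/CT. That depends on knowing which scans those are, and the two 45-day rules do not work together.

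**Working it through.** The documents state no expected concordance, share of men re-imaged or precision target, so there is no plan figure to reproduce. The check is a reading of the passages plus one piece of date arithmetic.

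**Step 1. Which pairings does Section 10 allow?** It uses both PET/CTs and any available routine-care scan.

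| Pairing | Could a released PET/CT result have influenced it? | Excluded by Section 10? |
|---|---|---|
| First PET/CT vs scan acquired before it | No | No |
| First PET/CT vs scan acquired after its release | Yes: scan may be prompted, or disease treated | No |
| Second PET/CT vs scan acquired before the first | Yes: about 6 months of management lies between | No |
| Second PET/CT vs scan acquired after the first was released | Yes: as in the second row | No |

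Only the first row is free of influence from disclosure. Section 10 permits all four and does not distinguish them.

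**Step 2. Which way would mixing move the rate?** Imaging prompted by a PET/CT finding could confirm sites that were discordant and raise concordance. Treatment between the scans could clear sites on later conventional imaging and lower it. The documents give no frequency for either, so neither sign nor size can be derived.

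**Step 3. Does a pre-PET comparator exist for every man?** Criterion 4 of Section 5.2 makes a completed bone scan and CT or MRI a condition of entry, so some earlier scan exists. Whether it is the intended comparator depends on the timing rules.

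**Step 4. Do the two timing rules agree?** Let S be the day of the qualifying staging scan, E the day of enrollment and P the day of the first PET/CT.

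- Section 5.2, criterion 4: E − S ≥ 45.
- Section 8 lists screening and consent before PET/CT: P − E ≥ 0.
- Adding these: P − S = (P − E) + (E − S) ≥ 0 + 45 = 45.
- Section 8, item 2, if the qualifying scan is the latest: P − S ≤ 45.

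Both hold only if P − S = 45, which forces E − S = 45 and P = E. The scan must be exactly 45 days old and PET/CT must be done on the day of enrollment. The one other route is a newer scan, which then becomes the latest. Criterion 3 of Section 5.2 uses the same 45-day wording for PSA, so the same arithmetic applies there. Section 8, item 2, also does not say that the imaging must precede the PET/CT.

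**The case against.** The best defense is that the documents already imply the pairing. Section 5.2 requires staging before entry, and Section 8, item 2, ties PET/CT to the latest bone scan and cross-sectional imaging. A natural reading is that these scans are the comparators for the first PET/CT. This narrows the gap but does not close it: item 2 is a scheduling rule, it gives no direction in time, and Section 10 neither cites it nor limits itself to those scans.

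It is also fair that this is a pilot with descriptive statistics, no designated primary endpoint and no decision threshold resting on concordance. That stands, and it sets the severity.

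Some stronger readings are tempting but unsupported:

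- **That Section 10 pools all scans.** It does not say so; its wording permits it.
- **That scans up to 44 months later will be scored against the first PET/CT.** The second PET/CT falls at 5 to 8 months (6, −1 to +2), and 36 more months give 41 to 44. That is a limit on data collection, which also serves the PSA and progression endpoint. It is not a stated comparison window.
- **That Appendix B gives the size of the effect.** Its 30 definite lesions on combined conventional imaging and 138 on PET/CT are counts, not lesion-matched, from 9 men with metastatic disease, with no scan timing. They are not a concordance rate for this population.
- **That the tissue analysis is faulty.** Section 10 keeps it separate and says the specimens come from routine follow-up. Calling it a selected subset is an optional reporting note.

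**Conclusion.** The point holds at **minor severity** for the Section 10 pairing. As worded, the concordance rate may mix a comparison uninfluenced by PET/CT with one that a released result helped to shape, and a cleaner headline comparison is available. This rests on the protocol's own statements that results are released and may prompt imaging or inform treatment; it does not assume that every later scan was prompted. Size and direction are unknown, and the study is not invalidated.

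The 45-day conflict **stands on its own as wrong as written**. Its arithmetic assumes only that PET/CT is not done before enrollment, as the order of Section 8 implies. The passages must be reconciled; which window applies is for the investigators to decide.

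Restricting to earlier scans removes influence from disclosure, but not differences due to elapsed time or treatment between scan and PET/CT. Nor does it settle the unit of concordance (lesion, region or patient) or clustering within a man. Those are related but separate gaps.

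**What to change.** 1. In Section 10, define the headline concordance rate as the first PET/CT against the latest bone scan and the latest CT or MRI acquired before it.
2. Report comparisons with imaging acquired after a result was released, and all comparisons involving the second PET/CT, separately and descriptively. State which scan counts when there are several.
3. Reconcile criterion 4 of Section 5.2 (and criterion 3 for PSA) with item 2 of Section 8, and say whether the imaging must precede the PET/CT, so that the comparator set is defined.
4. Optionally, describe the tissue results as coming from a selected subset.

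The cost is revised wording in three sections and fewer scans in the headline rate. No extra scans, biopsies or participants are needed, and the later comparisons are still reported.
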